7.3.3. Clinical Events Committee (CEC)

A clinical events committee (CEC) has been established with external experts who will adjudicate thromboembolic and major cardiovascular events. If deemed necessary, the same or a different CEC may also be requested to adjudicate other AEs of interest (e.g., for opportunistic infections, herpes zoster, malignancy). To allow for unbiased assessment, the CEC will remain blinded to treatment assignment. A CEC charter will describe the membership, scope of the CEC members' responsibilities, adjudication processes, and definitions used to review and assess specific AEs.

7.4. AE Reporting and Recording

7.4.1. AE Reporting

Timely, accurate, and complete reporting and analysis of safety information from clinical trials is crucial for the protection of patients and is mandated by regulatory agencies. Sponsor has established standard operating procedures in compliance with regulatory requirements worldwide to ensure appropriate reporting of safety information. All clinical trials sponsored by TBPH will be conducted in accordance with these procedures.

7.4.2. AE, SAE and AESI Recording

All AEs, regardless of seriousness, severity, or causal relationship to study medication, will be recorded from signing informed consent through the last study visit (or last subject contact in the case of a follow-up telephone call). AEs will be recorded on the AE page of the CRF. SAEs, regardless of relationship to study medication will be recorded from signing informed consent through the last study visit (or last subject contact in the case of a follow-up telephone call). Additionally, investigators may report SAEs assessed as related to study medication through 30 days following the last study visit (or last subject contact in the case of a follow-up telephone call). All SAEs will be recorded on both the SAE Report Form and the AE page of the CRF and should include the following:

Description of event:

- Signs and symptoms due to a common etiology should be reported as a single diagnosis; for example, cough, runny nose, sneezing, sore throat, and head congestion would be reported as "upper respiratory infection".
- A diagnosis or description must be as specific and as complete as possible (e.g., "lower extremity edema" instead of "edema").
- Hospitalization or surgical procedures should not be used as adverse event terms (e.g., if a subject was hospitalized for cholecystectomy due to cholecystitis, the adverse event term should be recorded as cholecystitis, and not as the procedure, cholecystectomy).
- "Death" should not be used as an adverse event term unless the cause of death is unknown. For events with a fatal outcome, the cause of death should be the adverse event term (e.g., if a subject died of an acute myocardial infarction, the adverse event term should be recorded as "Myocardial Infarction" and the event outcome as fatal).

- Relationship to study medication: The Investigator will make an assessment of the causal relationship of the study medication to the AE using the guidelines in Section 7.3.2.
- Severity: The severity of the AE will be assessed using the guidelines in Section 7.3.1.
- Outcome: The outcome of AEs will be recorded.
- Therapeutic measures: Measures taken for the treatment or management of the AEs will be recorded.

7.4.3. SAE and AESI Reporting Timeline

SAEs and AESIs (except for non-melanoma skin cancer) will be reported to Clinical Safety and Pharmacovigilance within 24 hours of the time the Investigator or his/her designee becomes aware that a SAE or AESI has occurred, whether or not the event is considered to be related to study medication. If the initial SAE is reported by telephone, a written report signed by the Investigator must be submitted within 24 hours.

The SAE/AESI Report Form must be completed in accordance with the SAE/AESI Report Form Completion Guidelines. If all information on the SAE/AESI Report Form is not available at the time of the initial report, follow-up SAE/AESI reports will be completed and submitted.

To report an SAE or AESI, complete and fax or email the appropriate Case Report Form to the following:

Theravance Biopharma Clinical Safety and Pharmacovigilance

[REDACTED]

For medical questions regarding an SAE or an AESI, contact the Sponsor's medical monitor by telephone as follows:

Medical Monitor Contact Information:

[REDACTED]

For fatal or life-threatening events, also fax copies of hospital case reports, autopsy reports, and other documents when requested. Additional information may be requested from the investigator to ensure the timely completion of accurate safety reports.

An SAE may qualify for reporting to regulatory authorities if the SAE is possibly attributable to the study drug and is unexpected/unlisted based on the current TD-1473 Investigator's Brochure. In this case, all investigators will receive notification of the event. The investigator is responsible for notifying the Institutional Review Board or Ethics Committee and documenting the notification, as required by local regulatory authorities and in accordance with the local institutional policy.

7.5. Adverse Event Follow-up

A subject experiencing an AE, SAE or AESI will be followed by the investigator or his/her trained delegate(s) through the follow-up visit or until the investigator and/or the Sponsor has determined that the AE, SAE or AESI has resolved or a stable clinical endpoint is reached, whichever is longer. The Sponsor may request follow-up of certain adverse events until resolution and documentation of assessments made during this period.

The investigator must take all therapeutic measures necessary for resolution of an SAE or an AESI. Any medications necessary for treatment of the SAE or AESI must be recorded in the concomitant medication section of the case report form.

8. STATISTICAL CONSIDERATIONS

8.1. General Considerations

All data for each subject will be listed as collected. All statistical summaries and analyses will be performed using [REDACTED]

Continuous data will be summarized using an 8-point summary (n, mean, standard deviation [SD], median, interquartile range [25% quartile, 75% quartile], minimum, and maximum) unless otherwise specified in the SAP or table shell. Categorical data will be summarized using counts and percentages.

Study Day 1 is defined as the day of the first study drug dose. The preceding day is Study Day -1.

Baseline is the last assessment (scheduled or unscheduled) obtained before start of study drug dosing, unless otherwise specified in the SAP (e.g., for fecal sample assessments). Baseline for endpoints that have more than one component is calculated from the individual component baselines, whether or not they were assessed during the same visit.

The study will include 2 formal database locks, one after all 160 subjects have either completed or withdrawn from the Induction phase, and one after all subjects have completed or withdrawn from the ATE phase. Separate SAPs will be prepared for the following unblinded analyses, and finalized before the database are locked for analysis:

Database lock after the Induction Phase is completed:

- Analyses of induction data, to include specifications for [REDACTED] [REDACTED] SAP, when not otherwise specified, refers to this SAP)

- [REDACTED]

- [REDACTED]

Database lock after the ATE phase is completed:

- Analyses of ATE data

Any changes to the data summaries and analyses outlined in this section will be described in the applicable SAP. Any major changes to the definition of the primary endpoint will also be included in a protocol amendment.

8.2. Sample Size and Power

Assuming that the less effective TD-1473 dose results in a 45-point improvement in placebo-adjusted CDAI score change at Week 12, the more effective dose results in a 60 point improvement, the residual SD is 100 points, and a sample size of 160 subjects with 60 subjects in each of the active dose groups and 40 subjects in the placebo group, 100,000 simulations performed using SAS/IML software yielded the following power estimates for 2-sided testing with the familywise Type I error rate controlled at 5% using the Hochberg step-up procedure:

- 82% power to show at least one of the two doses effective
- 58% power to show both doses effective

The target effect size of 60 points was selected as predictive of a clinically significant increase in clinical response rate. Of note, the study is not powered for the secondary endpoints.

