Sample Size:

Assuming that the less effective TD-1473 dose results in a 45-point improvement in placebo-adjusted CDAI score change at Week 12, the more effective dose results in a 60-point improvement, the residual SD is 100 points, and a sample size of 160 subjects with 60 subjects in each of the active dose groups and 40 subjects in the placebo group, 100,000 simulations performed using SAS/IML software yielded the following power estimates for 2-sided testing with the familywise Type I error rate controlled at 5% using the Hochberg -step-up procedure:

- 82% power to show at least one of the two doses effective
- 58% power to show both doses effective

The target effect size of 60 points was selected as predictive of a clinically significant increase in clinical response rate. Of note, the study is not powered for the secondary endpoints.

Study Efficacy Endpoints:

The primary endpoint is:

- CDAI score change from baseline at Week 12

The secondary endpoints are:

- CDAI clinical response (defined as reduction from baseline of ≥ 100 points or CDAI < 150) at Week 12
- CDAI clinical remission (defined as CDAI < 150) at Week 12
- SES-CD change from baseline at Week 12
- Endoscopic response (SES-CD reduction of $\geq 50\%$ from baseline or endoscopic remission) at Week 12
- SFAP clinical remission defined as abdominal pain score ≤ 1 (on a scale of 0-3), stool frequency ≤ 2.8 , and both not worse than baseline at Week 12

Study Safety Endpoints:

- Changes from baseline in vital signs, ECGs, and clinical laboratory results
- Incidence and severity of AEs

PROTOCOL SYNOPSIS (CONTINUED)

Analysis:

The primary analysis set for efficacy analyses will be a modified Intent-to-Treat (mITT) set: all randomized subjects who received study drug and had at least one postbaseline CDAI score. Efficacy data will be summarized by randomized treatment. The primary analysis set for general and safety analyses will be the Safety set: all randomized subjects who received study drug. Safety data will be summarized by treatment received.

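### The stated power of 82% / 58% cannot be reproduced from the stated inputs: it is about 1 to 2.5 points high, and a t-based calculation gives about 80% / 56%

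*Protocol*

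**What the plan says.** Protocol 8.2 assumes that the "less effective TD-1473 dose results in a 45-point improvement in placebo-adjusted CDAI score change at Week 12", that "the more effective dose results in a 60 point improvement" and that "the residual SD is 100 points". The sample is "a sample size of 160 subjects", made up of "60 subjects in each of the active dose groups and 40 subjects in the placebo group". Testing is "2-sided testing with the familywise Type I error rate controlled at 5% using the Hochberg step-up procedure". From 100,000 simulations it reports "82% power to show at least one of the two doses effective" and "58% power to show both doses effective".

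The synopsis repeats the inputs and both results. SAP 1.5 repeats the effects, SD, method and results, and SAP Table 3 gives the same 60/60/40 split. Protocol 8.5.4 and SAP 1.5 and 3.3.3 set out the Hochberg rule: both doses are declared if both p-values pass 0.05; otherwise the smaller p-value is compared with 0.025.

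Two things are not given. None of the three places allows for dropout, so the calculation reads as one with 160 evaluable subjects. None says which test statistic or model was simulated. SAP 1.5 refers to a separate sample size document for further detail.

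**The concern.** A power claim that comes with its effects, SD, group sizes and testing rule should come back when those inputs are run again. This one does not: both figures fall short, and the both-doses figure falls shorter. These are the only operating characteristics the plan states for its primary test, and they appear in three places. At stake is the accuracy of that statement and whether a reader can check it. Attrition is a separate matter and plays no part here, because every calculation below assumes that nobody is missing.

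**Working it through.** **Inputs.** n = 60, 60 and 40; effects 45 and 60; SD 100 (Protocol 8.2). Two-sided cut-offs are 0.05 when both doses pass and 0.025 otherwise (Protocol 8.5.4).

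**Step 1: standardised effects.**
- SE of each dose-minus-placebo difference = 100 × √(1/60 + 1/40) = 20.41.
- Expected z: 45/20.41 = 2.205 and 60/20.41 = 2.939.
- Correlation of the two statistics through the shared placebo arm = (1/40) / (1/60 + 1/40) = 0.6.

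**Step 2: each dose alone, normal approximation, Φ(expected z − critical value).**
- At 0.05 (critical value 1.960): Φ(0.245) = 59.7% and Φ(0.979) = 83.6%.
- At 0.025 (critical value 2.241): Φ(−0.037) = 48.5% and Φ(0.698) = 75.7%.

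**Step 3: Hochberg, known-variance z, bivariate normal with correlation 0.6.**
- Both doses: P(both z > 1.960) = 56.1%.
- At least one dose has two parts.
  - At least one z > 2.241: 48.5 + 75.7 − 44.4 (both above 2.241) = 79.9% from unrounded values.
  - Both z between 1.960 and 2.241: 1.0%.
  - Sum: 80.9%.

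**Step 4: estimated variance.** Simulation with at least 2 million trials per variant and the same Hochberg rule:

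| Calculation at 60/60/40, effects 45/60, SD 100 | At least one | Both |
|---|---|---|
| Stated in the plan | 82 | 58 |
| z, known variance | 80.9 | 56.1 |
| t, SD pooled over three arms (157 df) | 80.2 | 55.6 |
| t, pairwise (98 df) | 80.0 | 55.1 |

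Shortfall against the plan: 1.1 / 1.9 points (z), 1.8 / 2.4 (pooled t) and 2.0 / 2.9 (pairwise t).

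The planned analysis is a mixed model with Kenward-Roger degrees of freedom (SAP 3.3.4.2). It estimates the variance, so with complete data the pooled t is the closest simple match. The plan calls 100 the residual SD, so it would be double counting to add a further gain from baseline adjustment.

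**Step 5: can chance or rounding explain the gap?**
- Monte Carlo SE with 100,000 runs: √(0.80 × 0.20 / 100,000) = 0.13 point and √(0.56 × 0.44 / 100,000) = 0.16 point. The smallest shortfall, 1.1 points, is more than eight times its SE.
- To round to 82 and 58, the results must be at least 81.5 and 57.5. The best standard result is 80.9 / 56.1.

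**Step 6: which nearby inputs give about 82 / 58?**

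| Change | Test | At least one | Both |
|---|---|---|---|
| SD 98 | z | 82.4 | 58.1 |
| SD 97.5 | pooled t | 82.2 | 58.0 |
| Effects 46 and 61 | z | 82.2 | 58.1 |
| n = 63/63/42 (total 168) | pooled t | 82.1 | 57.9 |

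A change of 2 to 2.5% in the SD, of 1 point in the effects, or of 8 subjects in total restores both figures together. Two other readings were tried. Treating the comparisons as independent gives 88.5 / 50.0, which does not fit. Recalibrating Hochberg so that the familywise error is exactly 5% (nominal level about 0.0533) gives 81.6 / 57.3 with z. That is close, but the documents fix the cut-offs at 0.05 and 0.025.

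**The case against.** The strongest reply is that the comparison rests on settings chosen here. The plan does not name the simulated test, and the values 45, 60 and 100 look like rounded planning figures. Step 6 shows that very small departures from them recover both stated results at once. Monte Carlo error excludes chance, but it does not exclude an unrounded input or an unstated setting in the sample size document. Someone content with agreement to within two points could also say that the z-test reproduces both figures. And nothing in the design turns on the difference.

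Most of this stands. The cause cannot be settled from the protocol and SAP, so a reader might infer that the sponsor's simulation was wrong; the documents do not show that. Two parts do not stand. First, a two-point allowance is generous for a 100,000-run simulation. Only the known-variance z-test meets it on both figures; with the variance estimated, as the planned analysis does, the both-doses figure misses by 2.4 points. Second, if the simulation used other inputs, the plan's text still pairs 82% / 58% with inputs that do not produce them.

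**Conclusion.** The point holds, as a minor one. With 60/60/40 evaluable subjects, effects of 45 and 60 points, SD 100 and Hochberg at 0.05/0.025, power is about 80% for at least one dose and about 56% for both. The stated 82% / 58% is therefore about 1 to 2.5 points too high. This rests on normal data with a common SD, a shared placebo arm, no missing data and a standard z- or t-type test.

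A reader might go further and conclude that the trial is underpowered or needs the 168 subjects in Step 6. The documents do not support that. Power for at least one dose remains about 80%, the shortfall is no larger than the effect of a 2 to 2.5% error in the assumed SD, and sample size, allocation and testing procedure are unaffected.

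**What to change.** Check the source simulation in the sample size document.

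- If it used the stated inputs, restate the power as about 80% (at least one dose) and about 56% (both doses) in the synopsis, Protocol 8.2 and SAP 1.5.
- If it used a different test or unrounded values, keep 82% / 58% and state that test and the exact SD, effects and group sizes in the same three places.

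Either way, name the simulated test and say that all 160 subjects were taken as evaluable, if that was so. The cost is a change of wording in three places and, in the first case, a slightly less favourable stated figure. No patients are added and nothing in the design changes.

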8.3. Analysis Sets

The modified Intent-to-Treat (mITT) analysis set comprises all randomized subjects who receive at least one dose of study drug and have at least one postbaseline CDAI score. The mITT set is the primary analysis set for efficacy summaries and analyses.

The Per-Protocol (PP) analysis set comprises all subjects in the mITT analysis set with no major analysis protocol deviations (Section 8.3.2). If the number of mITT subjects excluded from the PP analysis set is ≤ 5 per treatment group, PP analyses will not be performed. Otherwise, both the mITT and the PP analysis set will be used for selected efficacy summaries and analyses.

The Safety analysis set comprises all subjects who receive at least one dose of study drug. The Safety analysis set will be the analysis set for both general (baseline, exposure, and compliance) and safety analyses.

[REDACTED]

Except for the [REDACTED] Analyses using the mITT analysis set will be by randomized treatment. Analyses using the PP analysis set and the Safety analysis set will be by actual treatment.

8.3.1. Examination of Subgroups

Predefined subgroups will include the following:

- Prior biologics failure (Yes, No)
- CDAI score at Screening Stage 2 (≤ 300 or > 300)

Others will be defined in the applicable SAP. For analysis purposes, prior biologics failure status and baseline CDAI score will be determined using the information captured in the clinical database rather than the information in the RTSM database.

For selected efficacy endpoints, results will be provided by subgroup.

8.3.2. Major Analysis Protocol Deviations

The following protocol deviations are considered major and as affecting analyses of efficacy data:

- [REDACTED]
- [REDACTED]
- [REDACTED]

Additional categories may be specified in the applicable SAP.

8.4. General Analyses

8.4.1. Demographics and Other Baseline Characteristics

Demographics and baseline characteristics including age, sex, race, ethnicity, creatinine clearance, weight, body mass index, CD characteristics, previous and current CD medications by category, and other medical history will be summarized.

8.5. Efficacy Analyses

8.5.1. Efficacy Endpoints

The primary endpoint is:

- CDAI score change from baseline at Week 12

The secondary endpoints are:

- CDAI clinical response (defined as reduction from baseline of ≥ 100 points or CDAI < 150) at Week 12
- CDAI clinical remission (defined as CDAI < 150) at Week 12
- SES-CD change from baseline at Week 12
- Endoscopic response (SES-CD reduction of $\geq 50\%$ from baseline or endoscopic remission) at Week 12
- Stool Frequency and Abdominal Pain (SFAP) clinical remission defined as abdominal pain score ≤ 1 (on a scale of 0-3), stool frequency ≤ 2.8 , and both not worse than baseline at Week 12

8.5.2. Primary Efficacy Evaluations

The primary analysis of CDAI score change at Week 12 will be performed by fitting a mixed effects repeated measures model to values at Weeks 4, 8, and 12, with baseline CDAI score as a covariate, using SAS procedure MIXED to fit a model with random subject effects, an unstructured covariance matrix, and including terms for prior biologics failure status, visit, and baseline CDAI score by visit and treatment by visit interactions.

The effect of each TD-1473 dose on reduction in CDAI at Week 12 (and also at Week 4 and at Week 8) will be estimated. These estimates are unbiased if missing data are missing at random (MAR). This assumption will be assessed with a missing data sensitivity analysis if at least one TD-1473 dose is shown to reduce Week 12 CDAI more than placebo.

As a sensitivity analysis, CDAI score change at Week 12 will also be analyzed by fitting the equivalent analysis of covariance (ANCOVA) model, using SAS procedure MIXED to fit an equal-slopes model with terms for prior biologics failure status, baseline CDAI score, and treatment.

8.5.3. Secondary and Exploratory Efficacy Evaluations

Binary efficacy endpoint rates will be compared using stratified Cochran-Mantel-Haenszel tests, stratifying by randomization stratum as determined from information in the clinical database. Selected binary endpoints will also be analyzed by fitting logistic regression models. Confidence intervals for treatment effects with nominal confidence level 95% will be calculated by methods specified in the SAP.

[REDACTED] and other efficacy endpoints assessed only at baseline and Week 12 will be analyzed by fitting an ANCOVA model like the one given for CDAI score change at Week 12. The covariate in each model will be the baseline value of the endpoint. [REDACTED]

[REDACTED] and other efficacy endpoints assessed at baseline and Weeks 4, 8, and 12 will be analyzed by fitting a mixed effects repeated measures model like the one given for CDAI score change at Week 12. The covariate in each model will be the baseline value of the endpoint. [REDACTED]

8.5.4. Multiplicity Adjustment

A Hochberg step-up procedure will be used for testing hypotheses associated with the primary efficacy endpoint (mean change in CDAI at Week 12):

Each TD-1473 dose will be compared with placebo. The null hypothesis will be that there is no difference between the TD-1473 dose level mean and the placebo mean, and the alternative hypothesis will be that they differ. To control the family-wise type 1 error rate at 5%, the Hochberg step-up procedure will be used:

- Step 1. If both p-values are ≤ 0.05 , reject both no-effect null hypotheses and conclude that both TD-1473 doses reduce the CDAI score at Week 12, compared to placebo; otherwise
- Step 2. If the smaller p-value is ≤ 0.025 , reject the no-effect null hypothesis for that dose; otherwise

Step 3. Fail to reject both no-effect null hypotheses and conclude that TD-1473 does not reduce the CDAI score compared to placebo.

[REDACTED]

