Continuous endpoints including score change will be analyzed by fitting analysis of covariance (ANCOVA) models which include terms for treatment, stratification factors, and baseline score as covariate. Mixed effects model repeated measures analyses will be used to analyze efficacy endpoints assessed at multiple postbaseline time points. Confidence intervals for means and mean differences with nominal confidence level 95% will be calculated by methods which will be specified in the Statistical Analysis Plan (SAP).

Binary efficacy endpoint rates will be compared using stratified Cochran-Mantel-Haenszel tests, stratifying by randomization stratum. Subjects with missing binary outcome will be counted as treatment failures. Confidence intervals for rates and rate differences with nominal confidence level 95% will be calculated by methods which will be specified in the SAP. Logistic regression models may be fitted for selected endpoints to evaluate dose-response curves.

A Hochberg step-up procedure will be used for hypothesis testing of the primary efficacy endpoint and the family-wise Type I error rate will be controlled at 5%. All comparisons will be 2-sided.

Safety data will be listed by subject and summarized by received treatment, showing subject counts for event data and means, medians, etc. for measurements.

Listings and summaries will be provided for demographics (age, sex, ethnicity, and race), baseline characteristics including baseline disease characteristics (e.g., extent of disease, duration of disease, complications) and treatment history, adverse events, laboratory tests, vital signs, and ECG data. Concomitant medications will be listed and summarized by received treatment.

SCHEDULE OF STUDY PROCEDURES

Table 1: Schedule of Study Procedures

Procedures	Screening Period		Treatment Period											Early Study Drug Discontinuation ^A	End of Study ^B (4 weeks post last study drug dose)	
			Induction (Day 1 to Week 12)					Active Treatment Extension (ATE Day 1 to ATE Week 48)								
Study Day/Week	Day -35 to -1		Day 1	W4	W8	W10	W12 ^C	ATE Day 1 ^D	ATE W4	ATE W8	ATE W16 ^E	ATE W24	ATE W36	ATE W48		
	Stage 1	Stage 2														
Hour Post-dose/Window				- 3 to + 5 days	0 to + 7 days	0 to + 3 days	1 – 7 days after W12	- 3 to + 5 days						0 to + 5 days	- 3 to + 5 days	
General Procedures and Safety Assessments																
Informed Consent	X															
Review Inclusion/Exclusion Criteria	X	X	X													

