3.3.3. Statistical Hypotheses

The primary estimate of interest, change from baseline in CDAI score at Week 12, is used to evaluate the effectiveness of therapy relative to the placebo comparator in the mITT population.

The following hypothesis testing schema will be employed to assess the primary endpoint: The null hypothesis for the treatment comparison will be that there is no difference between the mean responses at a given dose level of 1473 (active) and the mean response on the placebo treatment in change from baseline CDAI score at Week 12. The alternative hypothesis will be that there is a difference. Symbolically, this is expressed as follows:

$$H_0 : \mu_{Active} = \mu_{placebo}$$

$$H_1 : \mu_{Active} \neq \mu_{placebo}$$

In order to control for the comparison of 2 active treatment groups versus placebo for the primary endpoint, a multiplicity procedure is planned.

Only the primary endpoint is covered under multiplicity control and all other endpoints will be presented with nominal p-values.

A step-up Hochberg procedure will be used. The resulting nominal p-values for the primary endpoint will be ordered, largest to smallest.

If the largest p-value < 0.05 , then both treatment groups will be declared as statistically significant.

If the largest p-value is > 0.05 , then the smaller p-value will be compared to 0.025. If this p-value is < 0.025 , then the treatment group with the smaller p-value will be declared as statistically significant.

If no p-values meet the above conditions, the primary endpoint will be considered not statistically significant and the primary objective of the study was not met.

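### Protocol 8.5.4 reads a non-significant primary result as proof that TD-1473 does not reduce CDAI and, as a lesser point, infers a reduction from two-sided p-values without checking the sign

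*Protocol*

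**What the plan says.** Protocol 8.5.4 compares each dose with placebo on mean change in CDAI at Week 12. The null hypothesis is no difference, and "the alternative hypothesis will be that they differ". The synopsis adds that "All comparisons will be 2-sided". On error control: "To control the family-wise type 1 error rate at 5%, the Hochberg step-up procedure will be used".

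The three steps end as follows:

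- **Step 1** (both p-values at most 0.05): "reject both no-effect null hypotheses and conclude that both TD-1473 doses reduce the CDAI score at Week 12, compared to placebo".
- **Step 2** (smaller p-value at most 0.025): "reject the no-effect null hypothesis for that dose". No direction is stated.
- **Step 3** (otherwise): "Fail to reject both no-effect null hypotheses and conclude that TD-1473 does not reduce the CDAI score compared to placebo".

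SAP 3.3.3 applies the same procedure but words the result differently. If the larger p-value is below 0.05, "then both treatment groups will be declared as statistically significant". If nothing is rejected, the endpoint is called not statistically significant and the primary objective not met. It does not say that a dose reduces, or fails to reduce, CDAI. SAP 3.3.4.2 plans the LS mean difference from placebo with a 95% confidence interval for each dose.

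**The concern.** Step 3 contains two statements. Failing to reject is correct. Concluding that the drug does not reduce CDAI does not follow, because a non-significant result can leave the whole design effect inside the confidence interval. This is the sentence that answers the primary question, and Protocol 3.5.2 says the induction analysis is meant to inform the design of further studies. Protocol 8.5.2 and 8.9 also make the missing-data sensitivity analyses conditional on a dose having been shown to reduce CDAI.

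Step 1 has the opposite weakness. A two-sided p-value shows that the means differ, not which way. Lower CDAI is better, so a significant increase over placebo would literally be reported as a reduction.

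The two documents also end with different conclusions for the same negative result.

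**Working it through.** **Inputs.** Protocol 8.2 gives 60, 60 and 40 subjects, a residual SD of 100, true improvements of 45 and 60 points, two-sided Hochberg testing at 5%, and stated power of 82% (at least one dose) and 58% (both). In the simulations below, improvement over placebo is counted as positive. In the SAP's change-from-baseline scale it is a negative difference.

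**1. Reproducing the stated power.** The two contrasts share the placebo arm, so their correlation is (1/40)/(1/60 + 1/40) = 0.6. Simulating 1,000,000 trials under the Hochberg rule gives:

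| Version | At least one dose | Both doses |
|---|---|---|
| Protocol | 82% | 58% |
| Known variance (normal) | 80.8% | 56.1% |
| Pooled-variance t, 157 df | 80.2% | 55.7% |

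The simulation falls 1 to 2 points below the protocol for at least one dose and about 2 points below for both. That is close enough to show that the rule and inputs have been read correctly.

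**2. Step 3 when the drug works.** P(Step 3) = 1 − P(at least one rejection).

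- Protocol's own figure, effects 45 and 60: 1 − 0.82 = 18%.
- t-version simulation, effects 45 and 60: 1 − 0.802 = 19.8%.
- Effects 45 and 45 (my assumption): 36%.
- Effects 30 and 40 (my assumption): 55%.

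In every one of these cases both doses truly reduce CDAI, so the Step 3 conclusion is false. At the design effects, in 99% of the simulated trials that reach Step 3 the 95% confidence interval of at least one dose still contains 45 points.

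**3. A single example.** The standard error of a contrast is 100 × √(1/60 + 1/40) = 20.4 points. With normal quantiles, rejection at 0.025 needs a difference of 2.241 × 20.4 = 45.8 points, and the 95% interval has half-width 1.96 × 20.4 = 40.0 points. Suppose the better dose shows an observed improvement of 45 points and the other dose has p > 0.05. Then z = 45/20.4 = 2.20 and p is about 0.027, which exceeds 0.025, so the rule goes to Step 3. The interval is 45 ± 40, or 5 to 85 points. The plan would then conclude that TD-1473 does not reduce CDAI, although the estimate equals the effect described as "the less effective TD-1473 dose results in a 45-point improvement in placebo-adjusted CDAI score change at Week 12".

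**4. Step 1 with a wrong sign.** This is the probability that both p-values are at most 0.05 and at least one dose is worse than placebo (t version):

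| True improvements | Probability |
|---|---|
| 45 and 60 | about 0.0001% |
| 0 and 0 | 0.6% |
| 0 and 60 | 0.8% |

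**5. Effect of a sign condition.** Requiring the difference to favour TD-1473 leaves power at the design effects unchanged (80.2% and 55.7%).

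**The case against.** The strongest reply is that the SAP has already dropped both conclusions. Protocol 8.1 lets the SAP describe changes to the planned analyses, and SAP 3.3.3 speaks only of significance and of the objective not being met. This largely stands for the analysis itself. It does not remove the protocol sentence, and SAP 5.1, the section for changes from the protocol, records no change in the text supplied, so two different conclusions remain unreconciled.

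A second reply is that 18% is simply the type II error, which rewording cannot alter. That is true, and no error rate is claimed to be wrong. The issue is what is asserted when a type II error occurs: a statement that a reduction was not demonstrated would be correct in those trials, while the present one is false.

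Third, a wrong sign would be visible in the planned estimates and intervals, and the stated objective is improvement. This stands, and it is why the Step 1 point is minor.

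A reader might infer three stronger things that the documents do not support:

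- *That Step 2 and SAP 3.3.3 share the direction fault.* They declare only rejection or significance, which needs no sign condition.
- *That a harmful dose with p at most 0.05 inflates error by letting the other dose be tested at 0.05.* This is ordinary two-sided Hochberg. A dose with no effect is then claimed in the favourable direction with probability at most 2.5%, so there is no inflation to repair.
- *That wrong-direction claims could be common.* If one dose truly worsened CDAI by 45 points and the other improved it by 45, Step 1 would be met in 26% of trials. Nothing in the documents suggests such opposite effects.

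**Conclusion.** The point holds for Protocol 8.5.4. Step 3 is the substantive defect: it turns non-rejection into a conclusion of no reduction. That conclusion would be false in about 18% of trials under the protocol's own power, or about 20% by simulation, if the true effects are 45 and 60 points with SD 100 and 60/60/40 subjects analysed. Smaller true effects would make it false more often.

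The Step 1 wording is a minor defect: about 0.6% if neither dose works, 0.8% at 0 and 60 points, and effectively zero at the design effects. These figures use simple two-group contrasts in place of the planned repeated-measures model. The family-wise error rate, the thresholds, Step 2 and SAP 3.3.3 are sound.

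**What to change.** Keep the two-sided Hochberg tests as they are, and change the wording attached to them:

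1. In Step 1, and wherever Protocol 8.5.2 and 8.9 refer to a dose shown to reduce CDAI, require both rejection of the null hypothesis and an LS mean difference from placebo below 0.
2. Replace the Step 3 conclusion with a statement that a reduction in CDAI was not demonstrated, read with the 95% confidence intervals already planned in SAP 3.3.4.2.
3. Align Protocol 8.5.4 with SAP 3.3.3, including the boundary: the protocol uses ≤ 0.05 and ≤ 0.025, the SAP < 0.05 and < 0.025. Record the change in SAP 5.1.

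This takes a few sentences and needs no new data or analysis. Power at the design effects is unchanged. The one cost is a less definite negative conclusion.
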